### **Study design**

This is a single-center, prospective, comparative cohort study. The duration of the study is from 1/4/2023 to 1/12/2023. The study includes 90 patients (40 patients with symptomatic PVV without CVD, 40 patients with asymptomatic PVV and symptoms of CVD, 10 patients with lower limb varicose vein disease (CVD) without PVV).

### **Inclusion criteria:**

- Patient age group: 18-40 years;
- Presence of pelvic varicose veins according to DUS data;

- Reflux in the pelvic veins for more than 1 second before this DUS;
- Reflux in the superficial veins of the lower limbs.

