### **Rationale and basic information/ Abstract**

Currently, the term "varicose veins" implies not only the pathology of the superficial veins of the lower limbs, but also the pelvic veins. As yet, no epidemiological studies have investigated the frequency of the combination of pelvic and lower limb varicose veins, but in some studies the authors point to a combination of lower limb varicose veins and pelvic varicose veins (PVV) in 30-60% of patients. In this scenario, we are discussing the disease's clinically manifested forms, where lower limb varicose veins are visually identified and pelvic veins are identified by ultrasound and manifest as symptoms of pelvic congestion syndrome. There is no evidence of a concomitant occurrence of asymptomatic or latent forms of varicose veins in the lower limbs and PVV. (In these cases during duplex ultrasound angioscanning (DUS), pathological blood reflux is detected in the dilated superficial veins of the lower limbs and pelvis. However, there are no symptoms or signs of the disease.) As a result, it is not possible to assess the true prevalence of the combination of CVD and PVV.

At the same time, it is evident that dilatation and reflux in pelvic veins cannot but affect the clinical course of CVD in general and lower limb varicose vein disease in particular. Multiple studies from our clinic and foreign colleagues have substantiated this claim. It is caused not only by anatomical links between pelvic veins and lower limbs (perineal, clitoral perforating veins, tributaries of internal iliac veins), but also by common triggering mechanisms and similar pathogenesis of lower limb varicose vein disease and PVV.

Considering the above, valid questions arise about the effect of pelvic varicose veins with reflux on lower extremity venous outflow:

1. How does asymptomatic pelvic vein dilation with reflux impact venous outflow from the lower extremities and the clinical manifestations of CVD?
2. Does symptomatic pelvic vein dilation with reflux affect venous outflow from the lower limbs and clinical manifestations of CVD?
3. Does vulvar vein dilation affect venous outflow from the lower limbs and CVD clinical manifestations?
4. Is the severity or exposure of pelvic congestion syndrome a predictor for the development of lower limb venous outflow disorders?
5. How does the severity of clinical manifestations of PCS correspond to the severity of hemodynamic disturbance, as determined through instrumental research methods?

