### **Primary endpoint of the study**

To investigate the impact of varicose veins of the pelvis and pelvic congestion syndrome on the venous outflow of the lower limbs and the function of the muscular-venous pump of the lower limbs.

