**Exclusion criteria:**

- Menopause;
- Pregnancy;
- Postthrombotic syndrome;
- Suspicion of May-Turner syndrome;
- Ultrasound signs of nutcracker syndrome.

Before being included in the study, every patient signs a voluntary informed consent form to participate in the research.

The study enrolled 90 female patients, including 80 patients with PVV and 10 patients with CVD without PVV. All patients undergo a physician examination and receive DUS of pelvic veins and lower limbs, regardless of the presence or absence of clinical manifestations of diseases of pelvic veins and lower limbs. Then the patients are classified into three groups based on clinical and ultrasound evaluation. The first group (n=40) comprises patients with symptomatic PVV, including pelvic pain, dyspareunia, and heaviness in the hypogastrium, but without symptoms or signs of CVD. The second group (n=40) consists of women with asymptomatic PVV but with indications of CVD. The third group consists of 10 patients with varicose veins in the lower limb, without PVV or PCS symptoms. All patients undergo radionuclide venography of the lower limbs and emission computed tomography (SPECT) of the pelvic veins with *in vivo* labelled red blood cells (RBC). Quantitative indicators of the function of the lower extremity muscle-venous pump (MVP) and the pelvic venous congestion syndrome coefficient (Cpvc) are objectively assessed, using the results of radionuclide venography and single-photon emission computed tomography (SPECT). These indicators include average radiopharmaceutical transport time from regions of interest, and objectively represent blood venous flow from the veins of the lower extremities and the pelvis. Compression treatment using class 1 or 2 stockings is prescribed for patients with impaired venous outflow from the lower limbs and impaired venous evacuation function of the lower leg vein duct, depending on the class of CVD according to CEAP. Follow-up examinations, including clinical evaluations and radionuclide studies with SPECT of the pelvic veins, are performed 10 days after the initial clinical examination and radionuclide phlebography to evaluate the efficacy of the compression treatment.

Radionuclide venography with single-photon emission computed tomography (SPECT) of the pelvic veins and repeated clinical examinations are performed to evaluate the efficacy of the compression treatment 10 days after the initial clinical examination. Figure 1 displays the study's design.

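### The single inclusion list cannot be applied to the three planned groups: it bars all of group 3, and it forces leg reflux on group 1, so abnormal leg outflow there cannot be put down to pelvic disease alone

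*Protocol*

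**What the plan says.** The Inclusion criteria section is a single list of four items: an age range, "Presence of pelvic varicose veins according to DUS data", "Reflux in the pelvic veins for more than 1 second before this DUS" and "Reflux in the superficial veins of the lower limbs". No item is tied to a group, and nothing says that the items are alternatives.

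The groups are described elsewhere:

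- Study design labels group 1 as "40 patients with symptomatic PVV without CVD". The text after the Exclusion criteria describes the same 40 women as having pelvic symptoms "but without symptoms or signs of CVD".
- Group 2 (40 women) has asymptomatic PVV with CVD.
- Group 3 (10 women) has leg varicose veins and no PVV. Material and methods describes them as free of pelvic vein pathology.

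The Rationale section discusses "asymptomatic or latent forms of varicose veins in the lower limbs and PVV" and explains that in these cases "reflux is detected in the dilated superficial veins of the lower limbs and pelvis. However, there are no symptoms or signs" of disease. The primary endpoint is "To investigate the impact of varicose veins of the pelvis and pelvic congestion syndrome on the venous outflow of the lower limbs", together with muscle-pump function.

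**The concern.** An inclusion list fixes who is studied, and so what the results can be about. Here the list and the group descriptions point to different women. The protocol never says whether a group 1 patient must have, may have or must not have superficial leg reflux. These are three different populations.

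The primary question is whether pelvic disease impairs leg outflow. The Objectives section looks for predictors of impaired outflow in PVV patients without clinical CVD, and only group 1 supplies such patients. If all of them also have refluxing leg veins, a slow transport time has two candidate causes in the same limb. If the site quietly relaxes the list to fill the groups, group 1 becomes an undeclared mixture of women with and without reflux.

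**Working it through.** The protocol states no figure to reproduce on this point. The check sets each group definition against the list, with all items required.

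**Group sizes.** 40 + 40 + 10 = 90, which agrees with the stated total. PVV patients: 40 + 40 = 80.

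| Group | n | PVV on ultrasound (item 2) | Pelvic reflux (item 3) | Superficial leg reflux (item 4) |
|---|---|---|---|---|
| 1 | 40 | met by definition | compatible | compatible with the fuller definition; conflicts with a strict reading of the Study design label |
| 2 | 40 | met by definition | compatible | compatible |
| 3 | 10 | fails | fails | compatible |

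- Group 3: 10 of 90 (10/90 = 11%) cannot enter under the list.
- PVV patients allowed to have competent superficial leg veins: 0 of 80.

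**What each comparison can show if item 4 holds for everyone.**

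1. *Group 1 against the normal values.* The radionuclide venography description gives normal mean transport times of 6–8 s (tendon region), 10–12 s (muscle region) and 12–16 s (popliteal vein). A group 1 time above these could come from leg reflux, pelvic disease or both.
2. *Group 2 against group 3.* Both have CVD and they differ in PVV, so this contrast bears on the primary question. However, PVV in group 2 is asymptomatic, so it says nothing about pelvic congestion syndrome, and there are only 10 patients on one side.
3. *Group 1 against group 3.* These differ in pelvic disease and in clinical CVD at once, so neither is isolated.
4. *Congestion coefficient against transport time within group 1.* Reflux present in everyone is a constant and cannot by itself create a correlation. Its severity can vary. The Rationale section holds that pelvic and leg varicose disease share triggers and pathogenesis, so severity may rise with the coefficient and distort the relation.

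**Whether the information to resolve this is collected.** Diagnostics requires leg duplex ultrasound in every patient, and the method description says that it assesses the valves of the superficial veins. Venography is done on one limb, chosen by the side of the lesion, so the reflux status that matters is that of the imaged limb.

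**The case against.** The strongest defence is that the group 1 conflict is largely one of labels. Its fuller definition excludes clinical CVD, not reflux. The Rationale section recognises reflux without clinical expression, the Objectives section speaks of PVV without clinical CVD, and the secondary endpoint names subclinical CVD. A group 1 with silent reflux fits all of these, and only the short Study design label resists. This stands: a reader might infer that item 4 flatly contradicts group 1, but the documents support only a clash with that label and an undefined reflux status. It does not rescue the list, because group 3 fails items 2 and 3 on any reading.

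A second defence is that requiring reflux everywhere is restriction, a legitimate way to control a factor. This also stands in part. A reader might infer that leg reflux is inseparable from PVV in this design, or that the congestion coefficient can never be credited as a predictor. Neither follows. Group 3 has leg varicose veins without PVV, so on the literal reading reflux is constant across the groups rather than tied to PVV. Its presence cannot confound group contrasts or the within-group correlation; only its severity can.

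A third defence is that analysis by reflux status may sit in a statistical analysis plan that is not at hand. It may, but such a plan cannot repair eligibility criteria that exclude a planned group.

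**Conclusion.** The concern holds in limited form. The inclusion list is not stated per group and cannot be applied as written: it excludes all 10 group 3 patients and every PVV patient with competent superficial leg veins. This rests on reading the list as cumulative, which is its plain form. The group 3 failure shows that the site cannot be following it literally, so the actual reflux status of group 1 is unknown from the protocol.

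If all group 1 patients have reflux, three consequences follow: times above the norms cannot be attributed to pelvic disease alone, results do not extend to PVV without leg reflux, and the coefficient–transport time relation is open to distortion by reflux severity.

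The effect cannot be sized in seconds. The documents give neither the delay caused by superficial reflux nor the share of group 1 that would have it, so any figure for a shift in mean transport time would only restate its own assumptions.

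**What to change.** 1. State the inclusion criteria by group: PVV and pelvic reflux for groups 1 and 2 only; superficial leg reflux required in groups 2 and 3 and not required in group 1.
2. Record superficial reflux per limb from the existing duplex scan, and make sure that it is available for the limb imaged by venography.
3. Report group 1 transport time, and its relation to the congestion coefficient, by reflux status or adjusted for it. Attribute an effect to PVV alone only from reflux-free limbs. No group is free of venous disease, so that judgement would still lean on the stated normal values.
4. Reconcile the group descriptions in Material and methods, Study design, Inclusion criteria and the text after the Exclusion criteria.

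Barring reflux from group 1 altogether is possible but less attractive. It would remove the patients with subclinical CVD whom the secondary endpoint needs, and it would add reflux to the ways in which groups 1 and 3 differ.

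The cost is protocol wording and one recorded variable; no new examination is needed. The protocol date falls after the stated study start, so some women may already be enrolled. Their reflux status can be taken from the duplex record. The downside is that group 1 splits into two smaller subgroups whose sizes cannot be known in advance, and the reflux-free one may be small.

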**Exclusion criteria:**

- Menopause;
- Pregnancy;
- Postthrombotic syndrome;
- Suspicion of May-Turner syndrome;
- Ultrasound signs of nutcracker syndrome.

Before being included in the study, every patient signs a voluntary informed consent form to participate in the research.

The study enrolled 90 female patients, including 80 patients with PVV and 10 patients with CVD without PVV. All patients undergo a physician examination and receive DUS of pelvic veins and lower limbs, regardless of the presence or absence of clinical manifestations of diseases of pelvic veins and lower limbs. Then the patients are classified into three groups based on clinical and ultrasound evaluation. The first group (n=40) comprises patients with symptomatic PVV, including pelvic pain, dyspareunia, and heaviness in the hypogastrium, but without symptoms or signs of CVD. The second group (n=40) consists of women with asymptomatic PVV but with indications of CVD. The third group consists of 10 patients with varicose veins in the lower limb, without PVV or PCS symptoms. All patients undergo radionuclide venography of the lower limbs and emission computed tomography (SPECT) of the pelvic veins with *in vivo* labelled red blood cells (RBC). Quantitative indicators of the function of the lower extremity muscle-venous pump (MVP) and the pelvic venous congestion syndrome coefficient (Cpvc) are objectively assessed, using the results of radionuclide venography and single-photon emission computed tomography (SPECT). These indicators include average radiopharmaceutical transport time from regions of interest, and objectively represent blood venous flow from the veins of the lower extremities and the pelvis. Compression treatment using class 1 or 2 stockings is prescribed for patients with impaired venous outflow from the lower limbs and impaired venous evacuation function of the lower leg vein duct, depending on the class of CVD according to CEAP. Follow-up examinations, including clinical evaluations and radionuclide studies with SPECT of the pelvic veins, are performed 10 days after the initial clinical examination and radionuclide phlebography to evaluate the efficacy of the compression treatment.

Radionuclide venography with single-photon emission computed tomography (SPECT) of the pelvic veins and repeated clinical examinations are performed to evaluate the efficacy of the compression treatment 10 days after the initial clinical examination. Figure 1 displays the study's design.

1. *A clinical examination* comprises of complaints and medical history review, physical examination, checking of local vascular status and evaluating pain severity using the visual

analogue scale (VAS). VAS aids in identifying the severity of CPP. Additionally, to clinically assess the severity of CVD, the Revised Venous Clinical Severity Score (rVCSS) will be utilized. The clinical examination is conducted prior to DUS, radionuclide venography, and ECT. Then, after ten days of receiving compression treatment, the patients undergo a control clinical examination.

2. *Duplex ultrasound scanning (DUS)* of the lower limb veins is performed following a clinical exam to evaluate patency and status of the valve apparatus in the deep, superficial, and perforating veins. In addition to examining the veins in the limbs, DUS is used to assess the condition of the vulvar/perineal veins;
3. This is followed by *transabdominal and transvaginal ultrasound* of the pelvic veins, which includes assessing the patency of the pelvic, iliac, inferior vena cava and renal veins, measuring their diameters, determining the presence of blood reflux through the pelvic veins (gonadal, parametrial, uterine). The left renal vein (LRV) condition is analyzed by determining the vessel diameter at the point of intersection with the superior mesenteric artery and at the kidney gate. Blood flow velocity is measured at these locations, and the ratios of diameters and velocities are calculated to evaluate the degree of LRV stenosis.
4. *Radionuclide venography*. The procedure is performed using a gamma camera and integrated computer. While the patient is upright, 370 MBq of  $^{99m}\text{Tc}$  pertechnetate is injected into one of the dorsal veins of the foot after a tourniquet has been applied in the area of the ankle joint. With the assistance of a gamma camera detector, we track the transit of the radiopharmaceutical in the tibial (muscular-venous pump of the lower leg), popliteal, femoral, and iliocaval segments. During the investigation of the tibial pump, the patient performs flexion-extension movements in the ankle joint with a fixed heel to activate the calf pump. The gathered data is recorded on the magnetic-optical disk of the computer and then mathematically processed. To investigate the evacuation function of the muscular venous pump (MVP) of the leg an analytical computer program is used to identify areas of interest in the tendon, muscular portions of the leg veins, and the popliteal vein. Then, activity-time curves are constructed to estimate the evacuation time of the radiopharmaceutical from the MVP of the leg. This provides the average transportation time of the isotope. The average isotope transport time is inversely proportional to the volumetric velocity of blood flow. The longer the isotope's average transport time, the slower the blood flow velocity through the deep veins of the leg, and vice versa. Additionally, the rate of blood flow in the tibial veins is measured, providing information on the lower leg's MVP function. Analyzing a panoramic image of the veins from the foot to the inferior vena cava allows for an objective evaluation of deep vein patency and identification of any venovenous discharges that indicate pathology. Normally, only the deep veins in the examined limb are contrasted, while the saphenous and perforating veins are not visualized. The activity-time plot identifies the quick escalation and decline of isotope activity in the area of concern. The average time required to transport in the tendon area of the leg is normally 6-8 s, in the muscle part - 10-12 s, in the popliteal vein - 12-16 s.
5. *The single-photon emission computed tomography (SPECT) of the pelvic veins with in vivo-labelled red blood cells (RBCs)*. In order to assess the status of the pelvic veins with the radionuclide, 2 ml of Perfotech solution is injected into the cubital vein for the in vivo

labeling of red blood cells. After 20 minutes, 370 MBq of  $^{99m}\text{Tc}$ -pertechnetate is injected into one of the veins on the dorsum of the foot. Radionuclide venography is performed as described above. Twenty minutes after administering the radiopharmaceutical and RFG (the necessary time for  $^{99m}\text{Tc}$ -pertechnetate and autoerythrocytes to bind), single-photon emission computed tomography (SPECT) of the pelvic veins is conducted. The patient lies horizontally on her back, with the gamma camera detector centered above the womb. In order to obtain a tomographic image of the distribution of the labeled erythrocytes in the pelvic veins, 32 projections are made in a circular path with the gamma camera detector rotated 360°, using a 30-second exposure for each frame. The acquired information is analyzed using the SPECT Protocol software package, which generates sections in three projections (sagittal, transverse, and coronal) with a slice interval of 8 millimeters. The radiopharmaceutical utilized is non-reactive to the venous wall and does not stick to the vessels. The labeled red blood cells only amass in regions with heightened blood accumulation, such as varicose veins, liver, and spleen.

Normally, the gonadal veins are not contrasted, with either an absence or slight accumulation of radiopharmaceuticals in the pelvis venous plexus. To eliminate potential errors in the assessment of pelvic venous stasis, mathematical calculations of areas of interest are utilized due to the possibility of weak contrast of intrapelvic veins, caused by low activity of labeled red blood cells and errors in radiopharmaceutical administration. The gamma camera's computer equipment enables calculation of pulse numbers from the region of interest. The gamma camera captures radiopharmaceutical radiation activity in pulses per second, which quantitatively represents the content of labeled red blood cells within the region of interest. To ensure the objectivity of collected data, a ratio of pulse counts from two standard regions of interest is utilized - the veins of the uterus and parametrium, and the common iliac vein on each side. This is necessary as the speed of blood flow in pelvic veins can vary between patients. This ratio is known as the pelvic venous congestion coefficient (Cpvc). The labeled erythrocyte activity in this vessel remains the most stable value, while the activity of erythrocyte-phosphate-pertechnetate complexes in the venous plexuses relies on their varicose transformation and blood deposition. Normally, Cpvc does not exceed 0.5. An increase in this ratio indicates the presence of pelvic venous congestion due to stagnation of blood in the venous plexus of the pelvis. The higher the Cpvc, the more pronounced the pelvic venous congestion and stagnation of blood in the pelvic veins.

6. *Compression treatment.* Compression stockings of class 1 and 2 will be utilized as a method of compression therapy. The selection of compression class relies on the CVD classification as outlined by CEAP and the existence of impairments in the evacuation function of the lower extremity MVP in regards to the radiophlebography data of the lower limbs. The patient is instructed to wear these stockings for 10 consecutive days, 8 hours daily, following which repeated clinical and radionuclide examinations will be conducted to evaluate the efficacy of the treatment. The comfort level of the compression socks will be evaluated using a visual analog scale. This 10 cm long horizontal line assigns 1 point to each centimeter. Based on patient assessments, the following gradations of comfort will be identified: 9-10 points - complete absence of discomfort, comfortable wearing of the knitwear for 8 hours or more; 7-8 points - minor short-term mild discomfort (mild discomfort: a feeling of squeezing, sliding), which does not interfere with wearing the knitwear for 8 hours; 4-6 points - average severity of discomfort, the patient has difficulties using the stockings for 8 hours; 1-3 points - severe degree of discomfort, inability to use compression stockings.

Data from clinical examinations, ultrasound, and radionuclide studies are documented in the patient's personal medical record.

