**Study goal:**

- To study the status of venous outflow from the lower limbs and pelvis in patients with concomitant PVV and CVD.;
- To identify correlations between the degree of impairment of venous outflow from the pelvis and the severity of impairment of the lower extremity musculo-venous pump (MVP) as the main peripheral determinant of venous return from the lower limbs.;
- To study the influence of the duration and extent (involvement in the pathological process) of pelvic venous reflux on the degree of venous outflow disturbance of the lower limbs;
- To develop ultrasound and radionuclide criteria for the severity of pelvic congestion syndrome;

- To study the possibility of using the coefficient of pelvic congestion syndrome (Cpcs) as a predictor of venous outflow disturbance of the lower limbs;
- To establish the criteria for correcting venous outflow disturbances in the lower limbs with compression based on the severity of pelvic congestion syndrome;
- To evaluate the effectiveness of compression therapy for CVD in patients with PVV (PCS) and impaired venous outflow from the lower extremities and the musculo-venous pump function.

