## **Material and methods.**

This study enrolled 90 female patients, including 40 patients with PVV and PCS, 40 patients with combined PVV and CVD, and 10 patients with CVD without pelvic vein pathology.

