### **Treatments:**

Compression therapy with either class 1 or class 2 compression stockings will be administered to 90 patients with PVD and/or CVD. The selection of the compression class was based on the CEAP class and the severity of tibial MVP abnormalities according to radiophlebography data. The researcher will select the size of the compression product according to the standard scheme after verifying the diagnosis by pelvic and lower extremity vein DUS and radionuclide assessment of venous outflow from the pelvic and lower extremity veins (radionuclide venography and SPECT).

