These questions have significance not only in academic and scientific domains. They are directly related to the strategy and tactics of treating patients with a combination of varicose veins of

lower limbs and PVV, PCS and CVD, since the following fundamental issues have not yet been resolved:

1. Do asymptomatic patients with instrumental detection of PVV and lower limb varicose vein require correction?
2. Is it appropriate to utilize compression knitwear in patients with an asymptomatic course of instrumentally confirmed venous outflow disorders with a combination of pelvic and lower extremity varicose veins?
3. Can the coefficient of pelvic venous congestion be utilized as a quantitative indicator to prescribe compression treatment for venous outflow disorders in the lower limbs of asymptomatic patients without signs of CVD? In other words, can the coefficient of pelvic venous congestion be used as a reference index for correcting the evacuative function of the tibial MVP in patients without clinical manifestations of CVD?
4. How effective is compression in correcting impaired venous outflow from the lower limbs in PVV patients?

The severity of the clinical course of lower limb CPV is determined by objective symptoms such as pain, edema, trophic disorders, and venous ulceration. In patients with CVD, the severity of the disease course determines the development of pelvic congestion syndrome (PCS), which is manifested by chronic pelvic pain (CPP), hypogastric heaviness, and dyspareunia. CPP and dyspareunia are the main indicators of the severity of the clinical course of PCS. It has been demonstrated that PCS exacerbates the symptoms of CVD. Thus, correlating the severity of pelvic pain to the degree of pelvic venous fullness (coefficient calculated by pelvic venous scintigraphy) allows us to assume the presence of venous outflow disorders of the lower extremities. According to this hypothesis, the presence and severity of venous outflow disorders of the lower limbs can be determined not only by the results of instrumental examination of the pelvic and limb veins, but also by clinical assessment of the severity of CPP.

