### **Secondary endpoint of the study**

To assess the efficacy and comfort of utilizing compression stockings of class 1 and 2 in the treatment of lower limbs venous outflow disorders and correction of lower limb muscular-venous pump dysfunction in patients with PCS in combination with subclinical and clinically manifested lower limb CVD.

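### The secondary endpoint is set partly in women with pelvic congestion syndrome and manifest CVD, but the symptom-defined groups contain none (0 of 90), so group comparisons cannot isolate an effect of the syndrome

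*Protocol*

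**What the plan says.** The Protocol's secondary endpoint is the efficacy and comfort of class 1 and 2 stockings "in patients with PCS in combination with subclinical and clinically manifested lower limb CVD". The primary endpoint names the impact of both PVV and PCS on venous outflow from the limbs and on the muscular-venous pump.

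The rationale section describes PCS by its symptoms: "pelvic congestion syndrome (PCS), which is manifested by chronic pelvic pain (CPP), hypogastric heaviness, and dyspareunia". The group description, printed under Exclusion criteria, uses the same three symptoms to define group 1 and then adds "but without symptoms or signs of CVD". Of the next group it says: "The second group (n=40) consists of women with asymptomatic PVV but with indications of CVD". Group 3 is ten women with limb varicose veins and neither PVV nor PCS symptoms. Study design repeats the split: "40 patients with symptomatic PVV without CVD, 40 patients with asymptomatic PVV and symptoms of CVD".

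Other sections are looser. Material and methods lists "40 patients with PVV and PCS, 40 patients with combined PVV and CVD, and 10 patients with CVD without pelvic vein pathology", which leaves open whether the second 40 may also have PCS. One study goal is "To evaluate the effectiveness of compression therapy for CVD in patients with PVV (PCS) and impaired venous outflow from the lower extremities", where PVV and PCS look interchangeable. The study goals also plan radionuclide criteria for PCS severity and name a coefficient of PCS. The group description calls the SPECT ratio Cpvc a coefficient of the syndrome, and the SPECT item gives its normal upper limit as 0.5.

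**The concern.** If PCS means symptomatic disease, the half of the secondary-endpoint population with clinically manifested CVD has no members. The 40 women of group 2, who have PVV and manifest CVD, fall outside the endpoint as worded. Yet they are among those due to be treated: "Compression therapy with either class 1 or class 2 compression stockings will be administered to 90 patients with PVD and/or CVD". (The group description narrows treatment to women with impaired outflow, which does not change this point.)

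The same structure affects the PCS part of the primary endpoint. The study is described as a comparative cohort, and the statistical section lists only comparison tests (Fisher, Student, Mann-Whitney). A reader could easily take the difference between groups 1 and 2 as the impact of PCS, or group 2's response to compression as efficacy in PCS. The results are intended for ministry-level methodological recommendations, so either misreading could carry into practice.

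**Working it through.** **Inputs.** Group sizes and definitions come from Study design and the group description under Exclusion criteria. PCS is read by symptoms, as in the rationale section and the group 1 definition. The stated total reproduces: 40 + 40 + 10 = 90.

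**Step 1: code the groups.**

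| Group | n | PVV | PCS | Manifest CVD |
|---|---|---|---|---|
| 1 | 40 | 1 | 1 | 0 |
| 2 | 40 | 1 | 0 | 1 |
| 3 | 10 | 0 | 0 | 1 |

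**Step 2: cross-tabulate PCS and manifest CVD.**

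- Both: 0 of 90.
- PCS only: 40 (group 1).
- Manifest CVD only: 40 + 10 = 50 (groups 2 and 3).
- Neither: 0.

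The subclinical half of the secondary endpoint is covered by group 1, since the inclusion criteria ask for reflux in the superficial limb veins. Only the manifest half is empty.

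**Step 3: what the group means can tell.** Assume additive effects V (PVV), P (PCS) and C (manifest CVD) on mean transport time, with intercept a:

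- Group 1 mean = a + V + P
- Group 2 mean = a + V + C
- Group 3 mean = a + C

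Hence group 1 − group 2 = P − C, and group 2 − group 3 = V. There are three means and four unknowns. Adding any constant k to both P and C and subtracting k from a leaves all three means unchanged, so neither P nor C can be recovered. In matrix terms, PCS + CVD = 1 in every patient, their correlation is −1, and the matrix with intercept, PVV, PCS and CVD has rank 3 of 4. A row-space check confirms that P and C are not estimable, while P − C and V are. If PCS and CVD slowed outflow equally, groups 1 and 2 would show no difference at all.

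**Step 4: do the continuous measures fill the gap?** By the symptom definition, PCS is constant within each group. Any analysis within a group, or adjusted for group, therefore removes PCS presence entirely. Cpvc against transport time then describes degree of pelvic congestion. Pelvic pain on the VAS within group 1 describes severity among women who all have the syndrome. Neither is the effect of having PCS.

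**Step 5: precision of what remains.** Assumed: two-sided 0.05 and 80% power. The protocol gives 0.05 without a side and states no power.

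- Cpvc and transport time, groups 1 and 2 adjusted for group (n = 80): r = tanh[(1.960 + 0.842)/√(80 − 3 − 1)] = 0.31.
- Pain VAS within group 1 (n = 40): r = tanh[2.802/√37] = 0.43.
- Group 2 versus group 3: 2.802 × √(1/40 + 1/10) = 0.99 SD by the normal approximation, 1.01 SD by noncentral t.
- If group 2 were a mixture, PCS versus no PCS within it, by noncentral t: 0.91 SD at 20/20 and 1.05 SD at 10/30.

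**The case against.** **PCS may not mean symptoms.** The study goals and the SPECT item tie PCS to a radionuclide coefficient. On that reading, group 2 women with raised Cpvc could count as having PCS, and the number with both conditions would not be known until imaging. This stands as a limit: 0 of 90 is not true under every definition. It does not remove the point, because women are assigned to groups on clinical and ultrasound findings, and the rationale and the group 1 definition are symptom-based. That the protocol allows more than one reading is part of what needs correcting.

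**No analysis of group 1 versus group 2 as the PCS effect is stated.** Correct. The protocol names no such contrast, and its study goals and objectives speak largely of correlations and predictors. A reader might infer that the protocol plans the faulty comparison; the text does not say so. What stands is that the listed tests, applied to these groups, cannot deliver the PCS part of the primary endpoint.

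**The primary endpoint as a whole may seem lost.** It is not. The PVV part has a contrast in group 2 versus group 3. The objectives on PVV without clinical CVD fall within group 1, and the relation of pelvic congestion to limb outflow can still be studied.

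**Group 2 versus group 3 may seem biased unless adjusted for CVD severity.** The document does not support that as a flat statement. Its rationale holds that pelvic reflux affects the course of CVD, so severity may partly result from PVV, and adjusting for it could remove part of the effect sought.

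**Conclusion.** The point holds for PCS defined by symptoms, which is how the groups are formed. The manifest-CVD half of the secondary-endpoint population is then empty (0 of 90), and 40 women with PVV and manifest CVD are left outside it. PCS and manifest CVD are exact complements across all 90 women. Comparing group 1 with group 2 therefore yields only the PCS effect minus the CVD effect, and the effect of PCS presence on limb outflow is not estimable from group membership. The count needs no assumption beyond the symptom definition; the algebra adds additivity. No later analysis plan could cure this, since it cannot supply patients whom the group definitions exclude.

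The verdict does not extend to the PVV part of the primary endpoint or to the correlation objectives. Nor does it say that compression cannot be evaluated in group 2, only that such results would not be results in PCS. This should be corrected; it does not invalidate the study.

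**What to change.** 1. Reconcile Study goal, Material and methods, Secondary endpoint, Study design and the group description, and state one definition of PCS: by symptoms, or by Cpvc above the stated normal limit of 0.5.
2. With the groups as now defined by symptoms, reword the secondary-endpoint population to patients with PVV, with or without PCS, combined with subclinical (group 1) or clinically manifested (group 2) CVD. Report compression results separately by group, and draw no conclusion about PCS with manifest CVD.
3. State that group 1 versus group 2 does not estimate a PCS effect, and that the effect of PCS presence on limb outflow is not estimable from these groups.
4. Report Cpvc against transport time, within group or adjusted for group, as an effect of degree of pelvic congestion. Report pelvic pain VAS within group 1 as severity among symptomatic women.
5. Name group 2 versus group 3 as the contrast for asymptomatic PVV, shown unadjusted. Any adjustment for rVCSS or CEAP class should be a sensitivity analysis only.
6. If group 2 was in fact meant to include women with PCS, correct Study design and the group description instead, and compare by PCS status within group 2 using the examination and VAS already collected.

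Items 1 to 5 cost wording only: no extra patients or examinations, and all 80 women with PVV stay in the secondary endpoint. The downside is narrower conclusions about PCS. Item 6 also needs no new examinations, but its contrast would detect only large differences, about 0.9 to 1.05 SD at the splits shown above.
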